4.1. Protocol Deviations

Protocol deviations will be tracked by the study team throughout the conduct of the study in accordance with the Protocol Deviation Management Plan (PDMP) dated 10 January 2018 (Version 1.01). Protocol deviations classified as important are detailed in the PDMP and those requiring exclusion from the Per-Protocol (PP) population are detailed in [Appendix 1](#): Protocol Deviation Management and Definitions for Per Protocol Population.

A final blinded review of all deviations will take place at the database release stage to ensure all important deviations are identified as well as those leading to exclusion of the participant from the PP population.

Important protocol deviations and deviations which result in exclusion from the PP population will be summarised and listed. A separate listing of all inclusion/ exclusion criteria deviations based on data as recorded on the eligibility page of the eCRF will also be provided.

5. CONSIDERATIONS FOR DATA ANALYSES AND DATA HANDLING CONVENTIONS

5.1. Study Treatment & Sub-group Display Descriptors

Treatment Group Descriptions			
RandAll NG		Data Displays for Reporting	
Code	Description	Description	Order in TLF ^[1]
1	Placebo	Placebo	1
2	Mepolizumab 100mg SC	Mepolizumab 100mg SC	2

[1] TLF=Tables, Listings, Figures (as specified in [Appendix 12](#): List of Data Displays)

Treatment comparisons will be displayed as follows using the descriptors as specified:

Mepolizumab 100mg SC vs Placebo

5.2. Baseline Definitions

5.2.1. Visit-based endpoints

The co-primary endpoint of endoscopic NP score (based on centrally read data) is assessed at Screening (Visit 1) and Day 1 (Visit 2), the Screening value is used to confirm if a participant has met the criteria for randomisation. Baseline will be defined as the Day 1 value, if missing the immediately preceding centrally read value prior to Day 1 will be used.

For all other visit-based endpoints, Baseline will be defined as the latest non-missing measurement collected prior to the first dose of interventional product. This will generally be from the Day 1 assessment but may be from an unscheduled assessment.

Where time is collected, an assessment is valid for use as Baseline if the date and time is prior to or the same as the date and time of first dose. Where time is not collected, an assessment is valid for use as Baseline if the date of assessment is on or before the date of first dose.

5.2.2. eDiary Data

Participants report daily on the severity of individual and overall NP symptoms using an eDiary, this includes information for the co-primary endpoint of mean nasal obstruction VAS score. The baseline value for endpoints reported in the eDiary will be determined as the average score from the 7 days of diary data collected prior to Day 1 (using non-missing data recorded between Day -7 and Day -1 inclusive).

5.3. Multicentre Studies

In this multicentre global study, the number of enrolled participants and the number randomised to each treatment arm will be presented by centre, country and region.

Region will be included as a fixed effect covariate in the analysis models for efficacy endpoints (as detailed in Section 5.4). Countries have been grouped into the following regions with consideration for standard of care medical practice, number of participants enrolled and regulatory considerations.

Region	Countries
Europe (EU)	Germany, Netherlands, Romania, Sweden, UK
United States (US)	United States
Rest of World (RoW)	South Korea, Argentina, Australia, Canada, Russia

NOTE: Small numbers of participants in a treatment group within a region may result in model convergence issues, in these cases further combining of regions may be considered or if required exclusion of the region covariate.

5.4. Examination of Covariates, Other Strata and Subgroups

5.4.1. Covariates and Other Strata

Covariates to be included in the statistical analysis models of the co-primary efficacy endpoints:

- Randomised treatment group
- Region
- Baseline score
- Baseline \log_e blood eosinophil count

Covariates to be included in the statistical analysis model of time to first nasal surgery:

- Randomised treatment group
- Region
- Baseline total NP endoscopic score (based on centrally read data)
- Baseline nasal obstruction VAS
- Baseline \log_e blood eosinophil count
- Number of previous surgeries (1, 2, >2; as an ordinal variable)

Covariates to be included in the statistical analysis model of proportion of subjects with at least one course of systemic steroids for nasal polyps up to Week 52:

- Randomised treatment group
- Region
- Baseline total NP score (based on centrally read data)
- Baseline nasal obstruction VAS
- Baseline \log_e blood eosinophil count
- Number of OCS courses for NP in the previous 12 months (0, 1, >1, as an ordinal variable)

Section 7 provides full details of the analysis methods for each of the efficacy endpoints.

5.4.2. Examination of Subgroups

This section details the subgroups of interest within this study. For each co-primary endpoint, a separate exploratory analysis within each of the subgroup categories will be carried out. Subgroup analyses for all other endpoints are detailed in the statistical methods/analysis sections. Unless otherwise stated no formal hypothesis testing in subgroups of the population will be performed.

Subgroup	Categories
Participants with Asthma	Concurrent asthma, No concurrent asthma
Aspirin Exacerbated Respiratory Disease (AERDS)	Current AERDS, No Current AERDS
Number of previous surgeries	1, 2, >2
Baseline Blood Eosinophil Categories (GI/L)	≤0.3 GI/L; >0.3 to ≤0.5 GI/L; >0.5 to ≤0.7 GI/L; >0.7 GI/L
Region	Europe, United States, Rest of World
Age	18-<40, 40-<65, ≥65 years
Gender	Male, Female
Race	African American/African Heritage, White, Asian, Other

If, following unblinding, the analysis model within a subgroup category fails to converge due to small numbers of participants, the model will be rerun with consideration of further refining regions or if required exclusion of the region covariate. Failing this, subgroup categories may be further refined when possible, otherwise only a descriptive summary of the data will be presented. Footnotes will clearly identify the covariates included in the analysis model.

There is a biological rationale for potentially observing greater efficacy with increasing levels of baseline blood eosinophils. Except for baseline blood eosinophils, differential treatment effects are not expected for any of the other subgroups listed above and therefore any differences in efficacy of mepolizumab compared to placebo observed in subgroup categories will be viewed as exploratory.

5.5. Multiple Comparisons and Multiplicity

The treatment comparison of mepolizumab 100mg SC vs. placebo is of interest for the co-primary and secondary endpoints. Multiplicity arising from the multiple secondary endpoints will be controlled through testing of the secondary endpoints using a closed testing procedure according to the following pre-defined hierarchy:

1. Time to first nasal surgery
2. Change from baseline in overall VAS symptom score
3. Change from baseline in SNOT-22 total score
4. Proportion of subjects requiring systemic steroids for nasal polyps
5. Change from baseline in the mean composite VAS score (nasal obstruction, nasal discharge, mucus in the throat and loss of smell)
6. Change from baseline in mean individual VAS symptom score for loss of smell

For strong control of type I error, statistical significance for the first secondary endpoint in the pre-defined hierarchy will be dependent on statistical significance having been achieved for the two co-primary endpoints. Statistical significance for the subsequent secondary endpoints will be dependent on statistical significance having been achieved for the previous endpoints in the hierarchy.

For secondary endpoints, unadjusted p-values and p-values adjusted for multiplicity based on the above hierarchy, will be presented.

5.6. Other Considerations for Data Analyses and Data Handling Conventions

Other considerations for data analyses and data handling conventions are outlined in the appendices:

Section	Component
14.3	Appendix 3: Assessment Windows
14.4	Appendix 4: Study Phases and Treatment Emergent Adverse Events
14.5	Appendix 5: Data Display Standards & Handling Conventions
14.6	Appendix 6: Derived and Transformed Data
14.7	Appendix 7: Reporting Standards for Missing Data
14.8	Appendix 8: Values of Potential Clinical Importance

6. STUDY POPULATION ANALYSES

6.1. Overview of Planned Study Population Analyses

All displays will be based on the ITT population, unless otherwise specified.

Study population displays including summaries of subject disposition, protocol deviations, demographic and baseline characteristics, prior and concomitant medications and treatment exposure will be based on GSK Core Data Standards. Additional summary information showing the amount of time within the 52-week treatment period considered as on-treatment, off-treatment and missing will be presented.

A summary of subject disposition and duration of time spent in the no-treatment follow-up will be provided for the subset of participants who participated in the 6-month no-treatment follow-up.

Details of the planned displays are presented in [Appendix 12: List of Data Displays](#).

7. EFFICACY ANALYSES

Data reported up to Week 52 will be included in the analyses described in Section 7.1 to Section 7.4. Details of all planned displays are provided in Appendix 12: List of Data Displays and will be based on GSK data standards and statistical principles.

7.1. Primary Efficacy Analyses

7.1.1. Endpoint / Variables

The primary treatment effect to be estimated (estimand) will be the comparison of mepolizumab 100mg SC to placebo for the co-primary endpoints of:

- Change from baseline in total endoscopic NP score at Week 52 (based on centrally read data)
- Change from baseline in mean nasal obstruction VAS score during the 4 weeks prior to Week 52

Independent reviewers blinded to treatment, grade the total endoscopic NP score from image recording of endoscopies. The total score is reported as the sum of the right and left nostril scores and ranges from 0 to 8, with higher scores indicating greater disease severity.

Participants rate individual symptoms including nasal obstruction daily on a visual analogue scale (VAS) using an eDiary, the scale range is 0 (none) to 100 (as bad as you can imagine), with higher scores indicating greater disease severity, for analysis derived scores ranging from 0 to 10 are used (see Section 14.6.5).

Surgery/sinuplasty represents an intercurrent event as any nasal surgical procedure or dilatation of the air passages in the nasal cavity can affect subsequent scores for the co-primary endpoints. For analysis of the co-primary endpoints the intercurrent event of surgery/sinuplasty includes any procedure involving instruments resulting in incision and removal of tissue (e.g. polypectomy) or dilatation of the air passages (e.g. balloon sinuplasty) in the nasal cavity.

A composite strategy will be used for the intercurrent event of surgery/sinuplasty and a treatment policy strategy will be used for the intercurrent event of discontinuation of study medication. The study is designed to continue collecting data for participants who have prematurely discontinued from randomised treatment, off-treatment data collected for these participants will be included in the primary analysis.

Subjects who undergo surgery/sinuplasty prior to Week 52 will be assigned their worst observed NP score prior to the surgery/sinuplasty for the change from baseline value at Week 52 in total endoscopic NP score. Subjects who withdraw from study before Week 52 without having experienced surgery/sinuplasty will be assigned their worst observed NP score prior to study withdrawal.

Similarly, for the mean nasal obstruction VAS, subjects who undergo surgery/sinuplasty will be assigned their worst observed 4-week mean prior to surgery for change from baseline during the 4-weeks prior to Week 52. Subjects who withdraw from the study before Week 52 without having experienced surgery/sinuplasty will be assigned their worst observed 4-week mean prior to study withdrawal.

Sensitivity analyses to examine the impact of handling missing data as described above are detailed in Section 7.1.5.

7.1.2. Summary Measure

The summary measure of treatment effect will be the difference between mepolizumab and placebo in the variable medians.

7.1.3. Population of Interest

The primary population of interest for analysis of the co-primary endpoints is defined by the study inclusion/exclusion and randomisation criteria and is therefore the ITT population.

7.1.4. Strategy for Intercurrent (Post-Randomization) Events

The anticipated intercurrent events occurring prior to Week 52 for the co-primary endpoints are: Surgery/sinuplasty, which includes any procedure involving instruments resulting in incision and removal of tissue (e.g. polypectomy) or dilatation of the air passages (e.g. balloon sinuplasty) in the nasal cavity and premature discontinuation of interventional product.

For each co-primary endpoint, the anticipated intercurrent event of surgery/sinuplasty will be handled using a composite strategy such that the occurrence of the event is incorporated into the definition of the endpoint. In participants who do not experience surgery/sinuplasty, the anticipated intercurrent event of premature discontinuation of interventional product will be handled using a treatment policy strategy, such that in these participants all data reported at week 52 for total endoscopic NP score (or during the 4-week period prior to Week 52 for nasal obstruction VAS) will be included in the analysis, regardless of discontinuation from treatment.

7.1.5. Statistical Analyses / Methods

7.1.5.1. Statistical Methodology Specification

Endpoint / Variables

 Change from baseline in total endoscopic NP score (based on centrally read data) at Week 52 Change from baseline in mean nasal obstruction VAS score during the 4 weeks prior to Week 52
Model Specification

 For each co-primary endpoint, the p-value for the difference in median change from baseline

between treatments will be based on the non-parametric Wilcoxon rank-sum test.

- The difference in median change from baseline with 95% confidence intervals will be estimated by quantile regression using a bootstrap approach ([Keene, 2018], [Mehrotra, 2017]). The analysis model will include the following terms:

Fixed Categorical:	Treatment group, Region
Fixed Continuous:	Baseline score, Log _e baseline blood eosinophil count

- Participants with missing covariate information will be excluded from the analysis

Model Checking & Diagnostics

- Models will be checked for issues with convergence.

Model Results Presentation

- Median change from baseline within each treatment group.
- Estimated difference between treatments in median change from baseline with 95% confidence interval (CI).
- p-value comparing treatments groups from the Wilcoxon rank-sum test.
- A cumulative distribution function (CDF) plot will be provided for the change from baseline in endoscopic NP score at Week 52 by treatment group.

Subgroup Analyses

- Section 5.4.2 identifies the subgroups of interest for the co-primary endpoints.

Sensitivity and Supportive Analyses

For sensitivity and supplementary analyses, the same methodology as for the primary efficacy analysis will be used.

Sensitivity analyses

- For the primary analysis the change from baseline value for participants with surgery/sinuplasty or missing data at Week 52 (due to premature withdrawal from the study or another reason) will be based on the worst observed score prior to surgery/sinuplasty or study withdrawal respectively. The following sensitivity analyses will be carried out to examine the potential impact of choices for the handling of subjects with missing data and for the handling of data for subjects undergoing surgery/sinuplasty. Sensitivity analysis will be performed for each co-primary endpoint where:
 - a) change from baseline for subjects with missing data is based on the worst possible score across all subjects and change from baseline for subjects with surgery/sinuplasty is based on the worst observed score prior to surgery/sinuplasty.
 - b) change from baseline for subjects with surgery/sinuplasty or with missing data is based on the worst possible score across all subjects.

Supplementary analyses

- A supplementary analysis of each co-primary endpoint will be performed on the Per-Protocol (PP) population (see Appendix 1: Protocol Deviation Management and Definitions for Per Protocol Population).

7.2. Secondary Efficacy Analyses

For each secondary endpoint the primary treatment effect to be estimated (estimand) will be the comparison of mepolizumab 100mg SC to placebo.

7.2.1. Time to first nasal surgery

Evaluation of the key secondary endpoint of nasal surgery will be based on invasive procedures involving instruments resulting in incision and removal of tissue (polypectomy). Dilatation of the air passages in the nasal cavity (e.g. balloon sinuplasty) will not be included in this endpoint. Procedures occurring on the same date will be considered as part of the same surgery event. A clinical review will be carried out prior to the unblinding of treatment codes to identify all events to be considered as part of this evaluation.

The time to first nasal surgery will be determined as the number of days from the date of first dose of study medication to the date of first nasal surgery (see Section 14.6.5). If a participant withdraws from the study before Week 52 and before experiencing nasal surgery, the nasal surgery event time will be censored at the time of study withdrawal.

7.2.1.1. Summary Measure

The summary measure of treatment effect will be the hazard ratio, the ratio of hazards corresponding to treatment with mepolizumab compared with placebo. For this endpoint the hazard represents the probability of nasal surgery for a participant at a given point in time following first dose of interventional product, given the participant has not experienced the event prior to that time.

7.2.1.2. Population of Interest

The primary population of interest is the ITT population.

7.2.1.3. Strategy for Intercurrent (Post-Randomization) Events

A treatment policy strategy will be used for the intercurrent event of premature discontinuation of interventional product, such that available nasal surgery times will be included in the analysis regardless of whether the surgery occurred before or after discontinuation of interventional product.

7.2.1.4. Statistical Analyses / Methods

Endpoint / Variables					

 Time to first nasal surgery 					
Model Specification					

 Cox proportional hazards model with covariates as follows: 
 
 Fixed Categorical:	Treatment group, Region	
 
 Fixed Continuous:	Baseline total nasal polyps endoscopic score (centrally read data), Baseline nasal obstruction VAS, Log_e baseline blood eosinophil	
 
 		Fixed Categorical:	Treatment group, Region	Fixed Continuous:	Baseline total nasal polyps endoscopic score (centrally read data), Baseline nasal obstruction VAS, Log _e baseline blood eosinophil
Fixed Categorical:	Treatment group, Region				
Fixed Continuous:	Baseline total nasal polyps endoscopic score (centrally read data), Baseline nasal obstruction VAS, Log _e baseline blood eosinophil				

	count, Number of previous surgeries (1, 2, >2; ordinal)

 Participants with missing covariate information will be excluded from the analysis 	
Model Checking & Diagnostics	

 A log(-log(survival)) plot by treatment group will be used to assess the assumption of proportional hazards. 	
Model Results Presentation	

 The number of participants with an event, the number censored due to study withdrawal and at study completion will be presented by treatment arm. The hazard ratio with corresponding 95% CI and p-value from the Cox proportional hazards model will be presented. A summary and graph of the Kaplan-Meier estimate of the cumulative proportion of participants with nasal surgery within each treatment arm over time will be produced. 	
Subgroup Analyses	

 No subgroup analyses are planned for this endpoint. 	
Sensitivity and Supportive Analyses	

 Sensitivity analyses will be performed to assess the censoring-at-random assumption of the cox proportional hazards model where participants who withdraw from the study before experiencing surgery have their event times censored at the time of study withdrawal. Sensitivity analysis will be carried out where missing event times for participants randomised to mepolizumab who withdraw from the study before experiencing surgery will be imputed using a censoring-not-at-random method as described in [Jackson, 2014]. A step-change in event rate equivalent to a loss of benefit from mepolizumab will be imputed for these participants after their censoring time. This means a reduction in relative event rate equivalent to 1/(estimated treatment effect). Missing event times for placebo will imputed under a censoring-at-random assumption. 	

7.2.2. Change from Baseline in Mean Overall VAS Symptom Score During the 4 weeks Prior to Week 52, Mean Composite VAS Score and Mean Loss of Smell VAS Score

Change from baseline during the 4-weeks prior to Week 52 in mean overall VAS symptom score, mean composite VAS score (combining VAS scores for nasal obstruction, nasal discharge, mucus in the throat and loss of smell) and mean loss of smell score will be analysed as detailed for the co-primary endpoint of change from baseline in mean nasal obstruction VAS score.

7.2.2.1. Details regarding the summary measure, population of interest and the strategy for intercurrent events are provided in Section 7.1.2 to Section 7.1.4. Statistical Analyses / Methods

Endpoint / Variables

 Change from baseline in mean overall VAS symptom score during the 4 weeks prior to Week 52

 Change from baseline in mean composite VAS score (combining VAS scores for nasal obstruction, nasal discharge, mucus in the throat and loss of smell) during the 4 weeks prior to Week 52 Change from baseline in mean loss of smell VAS symptom score during the 4 weeks prior to Week 52 				
Model Specification				

 For each endpoint the p-value for the difference in median change from baseline between treatments will be based on the non-parametric Wilcoxon rank-sum test. The difference in median change from baseline with 95% confidence intervals will be estimated by quantile regression using a bootstrap approach. The analysis model will include the following terms: 
 
 Fixed Categorical:	Treatment group, Region	
 
 Fixed Continuous:	Baseline score, Log_e baseline blood eosinophil count	
 
 
 Participants with missing covariate information will be excluded from the analysis 	Fixed Categorical:	Treatment group, Region	Fixed Continuous:	Baseline score, Log _e baseline blood eosinophil count
Fixed Categorical:	Treatment group, Region			
Fixed Continuous:	Baseline score, Log _e baseline blood eosinophil count			
Model Checking & Diagnostics				

 Models will be checked for issues with convergence. 				
Model Results Presentation				

 Median change from baseline within each treatment group. Estimated difference between treatments in median change from baseline with 95% confidence interval (CI). p-value comparing treatment groups from the Wilcoxon rank-sum test. 				
Subgroup Analyses				

 No subgroup analyses are planned for this endpoint 				
Sensitivity and Supportive Analyses				

 No sensitivity/supportive analyses are planned for these endpoints 				

7.2.3. Change from Baseline in Sino-Nasal Outcomes TEST 22 (SNOT-22) Total Score at Week 52

The 22 questions of the SNOT-22 are each graded on a

CCI - This section contained Clinical Outcome Assessment data collection questionnaires or indices, which are protected by third party copyright laws and therefore have been excluded.

Details regarding the summary measure, population of interest and the strategy for intercurrent events are provided in Section 7.1.2 to Section 7.1.4.

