**NB: Courses of OCS or Surgery are not a reason for Study withdrawal or IP discontinuation.**

### **8.2.3. Primary reasons for IP discontinuation**

The primary reason for discontinuation of IP (and sub-reason, if applicable) will be categorized as:

- Adverse event
- Lost to follow-up
- Withdrew consent

[figure not shown]
- participant relocated
- frequency of visits
- burden of procedures
- other (specify)
- Protocol deviation
- Lack of efficacy
- Study closed/terminated
- Participant reached protocol-defined stopping criteria
  - Liver event
  - Pregnancy
  - QTc
- Investigator discretion

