### 10.1. Sample Size Determination

The sample size is based on the co-primary efficacy endpoints of total endoscopic nasal polyp score and nasal obstruction VAS score at Week 52 and the key secondary endpoint of time to actual surgery. A trial of 200 participants per treatment group is estimated to have over 90% power to observe statistical significance at the two sided 5% level for both co-primary endpoints and for the key secondary endpoint of time to actual surgery.

The calculation for the co-primary endpoints is based on analysis of study MPP111782. This analysis showed 27% of placebo participants with a one-point improvement in NP score compared to 52% of mepolizumab participants. For nasal blockage, 39% of placebo participants showed a one-point improvement in NP score compared to 70% of mepolizumab participants.

For surgery, 90% power to observe statistical significance at the two sided 5% level is based on a true reduction in the proportion of participants receiving surgery from 40% on placebo to 25% on mepolizumab. In the six month study MPP111782, 20% of participants on placebo and 9% of participants on mepolizumab received surgery; a greater proportion of participants receiving surgery is expected in this twelve month study.

The smallest observed effect predicted to result in a statistically significant difference between treatment groups is a reduction in the proportion of participants receiving surgery from 40% on placebo to 30% on mepolizumab.

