2.27.	ITT	SHELL	Analysis of Time to First Nasal Surgery	Footnote: Includes data reported up to Week 52	SAC [1]
2.28.	ITT	SHELL	Sensitivity Analysis of Time to First Nasal Surgery: Tipping Point Analysis	Footnote: Includes data reported up to Week 52	SAC [2]
2.29.	ITT	SHELL	Summary of Overall VAS Score	Footnote: Includes data reported up to Week 52	SAC [1]
2.30.	ITT	SHELL	Analysis of Median Change from Baseline Overall VAS Score (Weeks 49-52)		SAC [1]
2.31.	ITT	SHELL	Summary of SNOT-22 Total Score	Footnote: Includes data reported up to Week 52	SAC [1]
2.32.	ITT	SHELL	Analysis of Median Change from Baseline SNOT-22 at Week 52		SAC [1]
2.33.	ITT	SHELL	Summary and Analysis of Proportion of Subjects Requiring Systemic Steroids for Nasal Polyps up to Week 52	Footnote: Courses of systemic steroids separated by <7 days are considered a continuation of the same course Include n (%) with 0 vs ≥1 and 0, 1, 2, etc courses and total number of courses	SAC [1]
2.34.	ITT	SHELL	Subgroup Analysis of Proportion of Subjects Requiring Systemic Steroids for Nasal Polyps up to Week 52 by Participants with Asthma	Footnote: Courses of systemic steroids separated by <7 days are considered a continuation of the same course Include n (%) with 0 vs ≥1 and 0, 1, 2, etc courses and total number of courses	SAC [2]

CONFIDENTIAL

205687

Efficacy: Tables					
No.	Population	IDSL / Example Shell	Title	Programming Notes	Deliverable [Priority]
2.35.	ITT	SHELL	Summary of Composite VAS Scores	Footnote: Includes data reported up to Week 52 Subheaders: Composite - Nasal Symptoms [1] and Composite - Nasal Symptoms and Facial Pain [2] Footnote: [1] Composite - Nasal Symptoms includes nasal obstruction, nasal discharge, mucus in the throat and loss of smell [2] Composite - Nasal Symptoms and Facial Pain includes nasal obstruction, nasal discharge, mucus in the throat and loss of smell and facial pain	SAC [1]
2.36.	ITT	SHELL	Analysis of Median Change from Baseline Composite VAS Score - Nasal Symptoms (Weeks 49-52)		SAC [1]
2.37.	ITT	SHELL	Analysis of Median Change from Baseline Loss of Smell VAS Score (Weeks 49-52)		SAC [1]
2.38.	ITT	SHELL	Summary of P-values for Treatment Comparisons Adjusted for Multiplicity According to Hierarchy of Endpoints		SAC [1]
Other Endpoints					

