14.12.7. Efficacy Figures

Efficacy: Figures					
No.	Population	IDSL / Example Shell	Title	Programming Notes	Deliverable [Priority]
Co-Primary Endpoints					
2.1.	ITT	SHELL	Figure of Change from Baseline Total Endoscopic Nasal Polyps Score (Centrally Read) at Week 52	Show percentages in each category Programming Note: dataset with assigned values for subjects with surgery/missing data	SAC [1]
2.2.	ITT	SHELL	Figure of Median Change from Baseline Total Endoscopic Nasal Polyps Score (Centrally Read) by Visit	Median and 95%CI Footnote: Includes data reported up to Week 52	SAC [1]
2.3.	ITT	SHELL	Figure of Change from Baseline Total Endoscopic Nasal Polyps Score (Centrally Read) at Week 52: Cumulative Distribution Function	Programming Note: dataset with assigned values for subjects with surgery/missing data	SAC [2]

CONFIDENTIAL

205687

Efficacy: Figures					
No.	Population	IDSL / Example Shell	Title	Programming Notes	Deliverable [Priority]
2.4.	ITT	SHELL	Figure of Median Change from Baseline Total Endoscopic Nasal Polyps Score (Centrally Read) at Week 52: Primary and Sensitivity Analyses	Include primary and sensitivity analyses	SAC [2]
2.5.	ITT	SHELL	Figure of Change from Baseline Nasal Obstruction VAS Score (Week 49-52)	Show percentages in each category Programming Note: dataset with assigned values for subjects with surgery/missing data	SAC [1]
2.6.	ITT	SHELL	Figure of Median Change from Baseline Nasal Obstruction VAS Score in each 4-Weekly Period	Median and 95%CI Footnote: Includes data reported up to Week 52	SAC [1]
2.7.	ITT	SHELL	Figure of Median Change from Baseline Nasal Obstruction VAS Score (Week 49-52): Primary and Sensitivity Analyses	Include primary and sensitivity analyses	SAC [2]
Secondary Endpoints					
2.8.	ITT	SHELL	Kaplan-Meier Time to First Nasal Surgery	Footnote: Includes data reported up to Week 52	SAC [1]
2.9.	ITT	SHELL	Sensitivity Time to First Nasal Surgery: Tipping Point	Heat Map Footnote: Includes data reported up to Week 52	SAC [2]
2.10.	ITT	SHELL	Sensitivity Time to First Nasal Surgery: Tipping Point – MAR Assumption for Placebo	2-dimensional Footnote: Includes data reported up to Week 52	SAC [2]
2.11.	ITT	SHELL	Figure of Median Change from Baseline Overall VAS Score in Each 4-Weekly Period	Median and 95%CI Footnote: Includes data reported up to Week 52	SAC [1]
2.12.	ITT	SHELL	Figure of Median Change from Baseline SNOT-22 by Visit	Median and 95%CI Footnote: Includes data reported up to Week 52	SAC [1]

CONFIDENTIAL

205687

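### SAP 7.2.1.4 words the step-change for mepolizumab withdrawals as a reduction in surgery rate, but loss of benefit and the factor 1/HR require an increase; one sentence needs correcting

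*SAP*

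**What the plan says.** The endpoint is time to first nasal surgery, first in the secondary hierarchy (SAP 5.5 and 7.2.1). Participants who withdraw from the study before surgery are censored at withdrawal. SAP 7.2.1.1 fixes the direction of the effect measure: "The summary measure of treatment effect will be the hazard ratio, the ratio of hazards corresponding to treatment with mepolizumab compared with placebo". SAP 7.2.1.4 confirms what is reported: "The hazard ratio with corresponding 95% CI and p-value from the Cox proportional hazards model will be presented".

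Under Sensitivity and Supportive Analyses, SAP 7.2.1.4 questions the censoring-at-random assumption by imputing event times for mepolizumab participants who withdraw before surgery. The purpose is stated first: "A step-change in event rate equivalent to a loss of benefit from mepolizumab will be imputed for these participants after their censoring time". The next sentence turns it into a rule: "This means a reduction in relative event rate equivalent to 1/(estimated treatment effect"). Placebo withdrawals are imputed at random, with no shift. No other section corrects the rule, and the same sentence stands in the September 2019 plan included in the SAP file.

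The display list describes the output differently. Table 2.28 is titled "Sensitivity Analysis of Time to First Nasal Surgery: Tipping Point Analysis". Figure 2.9 is titled "Sensitivity Time to First Nasal Surgery: Tipping Point", with a programming note asking for a heat map, and Figure 2.10 is a tipping-point figure with placebo missing at random.

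**The concern.** The event is surgery, so a higher event rate is a worse outcome and benefit means a hazard ratio below 1. A participant who loses the benefit moves from the mepolizumab rate up to the placebo rate. The purpose sentence and the factor 1/HR both point that way. The word *reduction* points the other way.

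Followed literally, the rule gives participants who leave the mepolizumab arm a lower surgery rate than those who stay. The imputation would then move the hazard ratio away from 1 and would scarcely be able to overturn a significant primary result. A sensitivity analysis meant to question an assumption would instead reinforce the result that depends on it.

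**Working it through.** **Inputs.** Protocol 10.1: 200 participants per arm, two-sided 5%, and "a true reduction in the proportion of participants receiving surgery from 40% on placebo to 25% on mepolizumab", stated to give 90% power. Exponential surgery times over one year are assumed, to turn the proportions into hazards. The documents give no withdrawal rate.

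**Reproducing the plan's own figure.**
- Two proportions: (0.15 × √200 − 1.96 × √(2 × 0.325 × 0.675)) / √(0.40 × 0.60 + 0.25 × 0.75) = (2.121 − 1.298) / 0.654 = 1.259, so power is 0.896.
- Log-rank (Schoenfeld) with 80 + 50 = 130 events and HR 0.563: 0.574 × √(130/4) − 1.96 = 1.313, so power is 0.905.

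Both agree with the stated 90%, so these inputs are a fair basis for what follows.

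**Hazards.**
- Placebo: −ln(1 − 0.40) = 0.511 per year.
- Mepolizumab: −ln(1 − 0.25) = 0.288 per year.
- HR = 0.288 / 0.511 = 0.563, so 1/HR = 1.776.

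**The two readings of the rule.**
- Increase by 1/HR: 0.288 × 1.776 = 0.511, exactly the placebo hazard.
- Reduction by 1/HR: 0.288 / 1.776 = 0.162, which is 0.32 of the placebo hazard. Division is the only workable literal reading, because a rate cannot fall by 178%.

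The direction does not depend on the planning effect. For HR of 0.4, 0.5, 0.7 and 0.8, 1/HR is 2.50, 2.00, 1.43 and 1.25, always above 1, and HR × 1/HR = 1 returns the participant to the placebo hazard.

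**One participant who withdraws at mid-year.** The chance of an imputed surgery in the remaining six months is 1 − exp(−hazard × 0.5):
- censoring at random (0.288): 13.4%
- loss of benefit (0.511): 22.5%, the same as placebo
- literal reduction (0.162): 7.8%

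**Whole mepolizumab arm.** Suppose a share d of the arm would leave at mid-year if still without surgery. The expected one-year surgery proportion is 1 − [(1 − d) × 0.75 + d × 0.866 × S]. Here 0.866 is the chance of no surgery in the first half-year, and S is one minus the six-month figure above.

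| Assumed d | At random | Increase | Literal reduction |
|---|---|---|---|
| 5% | 25.0% | 25.4% | 24.8% |
| 10% | 25.0% | 25.8% | 24.5% |
| 20% | 25.0% | 26.6% | 24.0% |

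**Effect on the test.** This was simulated with 3,000 trials per rate, 200 per arm and exponential withdrawal of 5/10/20% by one year. Each trial used 20 imputations, its own estimated HR as the shift, and unadjusted Cox models combined by Rubin's rules.
- Average HR: 0.563/0.563/0.564 in the primary analysis, 0.573/0.583/0.605 with the increase, and 0.557/0.551/0.540 with the literal reduction.
- Of trials significant in the primary analysis, the increase overturns 1.7/3.0/8.0% and the literal reduction 0.0/0.1/0.0%. The Monte Carlo standard error is at most 0.6 points.

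The SAP's Cox model is covariate-adjusted and the imputation method it cites cannot be consulted here, so these figures give scale only.

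**The case against.** **The text largely resolves itself.** It names the purpose and the factor, and multiplying by that factor gives the right answer. A programmer reaches 0.162 only by dividing by the stated factor and ignoring the stated purpose. This stands, and it is the main reason for calling the point minor. It does not make the sentence correct: this is the only place in the SAP text that gives the numerical rule, and its direction is wrong.

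**This is not shown to be the only check.** A reader might infer that, with the rule as worded, the key secondary endpoint has no working test of informative censoring. The documents do not support that. SAP 7.2.1.4 speaks of sensitivity analyses in the plural. The tipping-point table, heat map and placebo-at-random figure point to a range of shifts, and a tipping-point search has to move towards loss of significance. The range itself cannot be seen, because the shells are not included (SAP 14.13).

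**Few participants may be affected.** Protocol 8.2.2/8.2.3 notes: "Courses of OCS or Surgery are not a reason for Study withdrawal or IP discontinuation". That may keep withdrawals low, although no rate is given. A reader might add that Protocol section 8 asks participants to agree to contact about surgery after withdrawal, and so expect fewer imputed cases. That does not follow, because SAP 7.2.1 and 14.6.5 censor at study withdrawal and do not say that later contact extends follow-up.

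**Conclusion.** The sentence is wrong as written. With the effect defined as mepolizumab over placebo and HR below 1, the rate after withdrawal must rise by 1/HR to the placebo hazard. At the planning effect the rule should impute 0.511 per year; read literally it imputes 0.162. The contradiction lies within SAP 7.2.1.4 and needs no outside source. It applies whenever the estimated HR is below 1, the only case in which there is a benefit to lose.

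The severity is minor. The primary Cox test, the alpha and the hierarchy do not change, and no success criterion depends on this analysis. The average shift in HR is small at every withdrawal rate tried: at most from 0.564 to 0.605 with the correct rule and to 0.540 with the literal one. Those rates are assumptions, as are the exponential times and the unadjusted model. It would be going too far to conclude that the surgery result itself is unreliable.

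The tipping-point titles are a secondary clarification, not a second error: the SAP text gives one shift and does not state the grid that such displays need.

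**What to change.** Replace the sentence in SAP 7.2.1.4 with: *After censoring, the hazard for mepolizumab withdrawals is multiplied by 1/(estimated hazard ratio), i.e. increased to the placebo hazard when the hazard ratio is below 1.*

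For Table 2.28 and Figures 2.9 and 2.10, state the grid of shifts in the SAP or cross-refer to the shell that holds it. Do not retitle these displays to a single shift, because that could drop a tipping-point analysis that the display list evidently plans.

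The cost is one sentence and one cross-reference (or a short statement of the grid). No new data are needed, and nothing changes in the design or the primary analysis.
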